- 13. Severe hepatic impairment based upon medical history and laboratory abnormalities (eg, low albumin and abnormal bilirubin levels)

- 14. Any of the following abnormalities in clinical laboratory test results at Screening, as assessed by the study-specific laboratory and confirmed by a single repeat test, if deemed necessary:
  - Absolute neutrophil count of less than the lower normal range of the Central Laboratory (LNR) i.e. 1.7 x 10^9/L (1700/mm^3)
  - Hemoglobin of less than 10.0 g/dL or hematocrit less than 30%
  - Platelet count of less than 100,000 mm^3
  - Absolute lymphocyte count of less than the lower normal range of the Central Laboratory (LNR) i.e. 0,9 x 10^9/L (900/mm^3)
  - Total bilirubin greater than 1.5 × the upper limit of normal (ULN); patients with a history of Gilbert's syndrome may have direct bilirubin measured and would be eligible for this study provided the direct bilirubin result is less than or equal to the ULN
  - Alanine aminotransferase or aspartate aminotransferase greater than  $2.5 \times$  the ULN
  - Serum creatinine greater than or equal to 1.5 mg/dL. For patients with a value of greater than or equal to 1.5 mg/dL, if their creatinine clearance is at least 60 mL/min (calculated using the Chronic Kidney Disease Epidemiology Collaboration creatinine equation), enrollment may be allowed.
- 15. History or evidence of hepatitis B virus infection at Screening. Patients with a positive hepatitis B surface antigen result are excluded. For patients with an isolated positive antihepatitis B core antibody result, the hepatitis B surface antibody result must also be positive to be eligible for this study.
- 16. History or positive test result for hepatitis C virus (HCV) antibody, indicating ongoing infection, at Screening. Confirmatory testing for HCV RNA will be conducted for patients who have a positive test result. Patients who have a negative result for HCV RNA will be eligible to participate in the study.
- 17. History of positive HIV test result or congenital or acquired immunodeficiency (eg, common variable immunodeficiency disease). Patients who are positive for HIV antibodies (HIV-1 or HIV-2) at Screening are excluded from the study.
- 18. Suicidal ideation or behavior in the past 12 months as indicated by a positive response (yes) to question 4 or 5 on the C-SSRS completed at the Screening visit or at Baseline
- 19. Pregnant or breastfeeding

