#### 11.7 The Columbia-Suicide Severity Rating Scale

The C-SSRS, Investigator-administered version, was designed to provide a prospective, standardized measure of suicidality. The scale allows clinicians and researchers alike to assess the severity and lethality of suicidal behaviors and ideations and can be used to monitor treatment outcomes and establish suicide risk in a variety of research and clinical settings. Requiring approximately 5 minutes for completion, the C-SSRS is administered in the form of a clinical interview.

This C-SSRS is available in 2 versions: 1 for use at screening referring to the past year and 1 for use throughout the rest of the study referring to the time since the prior visit.

If at screening or baseline there are "yes" answers on item 4 or 5, the patient will not be included in the study.

Any patient with a positive response at subsequent visits (answers "yes" to questions 1-5) should be referred to a mental health specialist (psychiatrist or clinical psychologist) for further evaluation, and the study medication should be paused. After a mental health specialist evaluation, the final decision on restarting or permanently discontinuing study treatment will be at the discretion of the Investigator in consultation with the mental health specialist. These cases should be reported as an AESI. Refer to Section 11.8.2.

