## **17 APPENDIXES**

The assessments and scales included in the appendixes are samples of what may be used during the study. The study-specific assessments and scales may be different.

- Appendix 1. Rajka and Hanifin Criteria for Atopic Dermatitis
- Appendix 2. Eczema Area Severity Index (EASI)
- Appendix 3. Investigator Global Assessment for Atopic Dermatitis (IGA-AD)
- Appendix 4. Body Surface Area
- Appendix 5. Peak Pruritus Numerical Rating Scale
- Appendix 6. Skin Pain Numerical Rating Scale
- Appendix 7. Sleep Disturbance Numerical Rating Scale
- Appendix 8. Patient Oriented Eczema Measure (POEM)
- Appendix 9. Patient Global Impression of Severity (PGIS) Scale
- Appendix 10. Patient Global Impression of Change (PGIC) Scale
- Appendix 11. Dermatology Life Quality Index (DLQI)
- Appendix 12. Pulmonary Status NRS in Patients with Asthma
- Appendix 13. The Columbia-Suicide Severity Rating Scale (C-SSRS)
- Appendix 14. The Hospital Anxiety and Depression Scale (HADS)
- Appendix 15. Protocol Amendment Summary

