# Appendix 13: The Columbia-Suicide Severity Rating Scale

# For Screening

SUICIDAL IDEATION		
Ask questions 1 and 2. If both are negative, proceed to "Suicidal Behavior" section. If the answer to question 2 is "yes", ask questions 3, 4 and 5. If the answer to question 1 and/or 2 is "yes", complete "Intensity of Ideation" section below.	Lifetime: Time He/She Felt Most Suicidal	Past 12 Months

 
1. Wish to be Dead
 
Subject endorses thoughts about a wish to be dead or not alive anymore or wish to fall asleep and not wake up.
 
Have you wished you were dead or wished you could go to sleep and not wake up?
 
If ves, describe:
 
	Yes No	Yes No

 
2. Nonspecific Active Suicidal Thoughts
 
General nonspecific thoughts of wanting to end one's life/die by suicide (e.g., "I've thought about killing myself") without thoughts of ways to kill oneself/associated methods, intent, or plan during the assessment period. Have you actually had any thoughts of killing yourself?
 
If yes, describe:
 
	Yes No	Yes No

 
3. Active Suicidal Ideation with Any Methods (Not Plan) without Intent to Act
 
Subject endorses thoughts of suicide and has thought of at least one method during the assessment period. This is different than a specific plan with time, place or method details worked out (e.g., thought of method to kill self but not a specific plan). Includes person who would say, "I thought about taking an overdose, but I never made a specific plan as to when, where or how I would actually do it…and I would never go through with it."
 
Have you been thinking about how you might do this?
 
If yes, describe:
 
	Yes No	Yes No

 
4. Active Suicidal Ideation with Some Intent to Act, without Specific Plan Active suicidal thoughts of killing oneself and subject reports having some intent to act on such thoughts, as opposed to "I have the thoughts, but I definitely will not do anything about them." Have you had these thoughts and had some intention of acting on them? If yes, describe:
 
	Yes No	Yes No

 
5. Active Suicidal Ideation with Specific Plan and Intent Thoughts of killing oneself with details of plan fully or partially worked out and subject has some intent to carry it out. Have you started to work out or worked out the details of how to kill yourself? Did you intend to carry out this plan? If yes, describe:

	Yes No	Yes No

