nain or how you were feeling)		
(0) Does not apply		

SUICIDAL BEHAVIOR		
(Check all that apply, so long as these are separate events; must ask about all	Lifetime	Past 12 Years
types)	Vos No	Vac No
A potentially self-injurious act committed with at least some wish to die. $as a$	165110	165100
result of act. Behavior was in part thought of as method to kill oneself. Intent		
does not have to be 100%. If there is anv intent/desire to die associated with		
the act, then it can be considered an actual suicide attempt. There does not		
have to be any injury or harm, just the potential for injury or harm. If person		
pulls trigger while gun is in mouth, but gun is broken so no injury results, this		
is considered an attempt.		
Inferring Intent: Even if an individual denies intent/wish to die, it may be		
inferred clinically from the behavior or circumstances. For example, a highly		
lethal act that is clearly not an accident so no other intent, but suicide can be		
inferred (e.g., gunshot to head, jumping from window of a high floor/story).		
Also, it someone denies intent to die, but they thought that what they did could		
be lethal, intent may be inferred.		
Have you made a suicide allempi: Have you done anything to have yourself?	Total # of	Total # of
Have you done anything to harm yoursey. Have you done anything dangerous where you could have died?	Attempts	Attempts
What did you do?	racinpus	ruempts
Did vou as a way to end your life?		
Did you want to die (even a little) when you ?		
Were you trying to end your life when you?		
Or did you think it was possible you could have died from?		
Or did you do it purely for other reasons / without ANY intention of killing		
yourself (like to relieve stress, feel better,		
get sympathy, or get something else to happen)? (Self-Injurious Behavior		
without suicidal intent)		
If yes, describe:	Vec No	Vec Ne
Has subject engaged in Non-suicidal Self-Injurious Behavior?	165 100	165 10
Ins subject engaged in 1 on success of injurious Denvior .		
Interrupted Attempt:	Yes No	Yes No
When the person is interrupted (by an outside circumstance) from starting the		
potentially self-injurious act (if not for that, actual attempt would have		
Occurred).		
overdose. Person has phis in hand but is stopped from ingesting. Once they ingest any pills, this becomes an attempt rather than an interrupted attempt		
Shooting: Person has gun pointed toward self, gun is taken away by someone		

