include anything beyond a verbalization or thought, such as assembling a         specific method (e.g., buying pills, purchasing a gun) or preparing for one's         death by suicide (e.g., giving things away, writing a suicide note).         Have you taken any steps towards making a suicide attempt or preparing to         kill yourself (such as collecting pills, getting a gun, giving valuables away or         writing a suicide note)?         If yes, describe:         Suicidal Behavior:         Suicidal behavior was present during the assessment period?
specific method (e.g., buying pills, purchasing a gun) or preparing for one's       Total # of         death by suicide (e.g., giving things away, writing a suicide note).       Total # of         Have you taken any steps towards making a suicide attempt or preparing to       preparatory         kill yourself (such as collecting pills, getting a gun, giving valuables away or       Total # of         writing a suicide note)?       If yes, describe:
death by suicide (e.g., giving things away, writing a suicide note).       Total # of         Have you taken any steps towards making a suicide attempt or preparing to       Total # of         kill yourself (such as collecting pills, getting a gun, giving valuables away or       Total # of         writing a suicide note)?       If yes, describe:
Have you taken any steps towards making a suicide attempt or preparing to kill yourself (such as collecting pills, getting a gun, giving valuables away or writing a suicide note)?       preparatory acts       preparatory acts         If yes, describe:
kill yourself (such as collecting pills, getting a gun, giving valuables away or writing a suicide note)?       acts       acts         If yes, describe:
writing a suicide note)?       If yes, describe:
If yes, describe:
Suicidal Behavior:     Yes No       Suicidal behavior was present during the assessment period?     Image: Comparison of the second se
Suicidal Behavior: Yes No Yes No Suicidal behavior was present during the assessment period?
Suicidal behavior was present during the assessment period?
Answer for Actual Attempts Only Most Lethal Most Lethal Most Lethal
Attempt Attempt Attempt
Date: Date: Date:
Actual Lethality/Medical Damage:
0. No physical damage or very minor physical damage (e.g., Enter Code Enter Code Enter Code
surface scratches).
1. Minor physical damage (e.g., lethargic speech; first-degree
burns; mild bleeding; sprains).

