12.7. The Columbia-Suicide Severity Rating Scale

The C-SSRS, investigator administered version, was designed to provide a prospective, standardized measure of suicidality. The scale allows clinicians and researchers alike to assess the severity and lethality of suicidal behaviors and ideations and can be used to monitor treatment outcomes and establish suicide risk in a variety of research and clinical settings. Requiring approximately 5 min for completion, the C-SSRS is administered in the form of a clinical interview. This C-SSRS is available in 3 versions:

For this study we are using the following versions: For screening: Lifetime/Recent version and for the remaining part of the study: Since Last Visit version.

C-SSRS will be collected at different time points as per the SoA in Protocol Section 9.

The C-SSRS categories have been re-ordered from the actual scale to facilitate the definitions of the endpoints, and to enable clarity in the presentation of the results: Category 1 – Wish to be Dead, Category 2 – Non-specific Active Suicidal Thoughts, Category 3 – Active Suicidal Ideation with Any Methods (Not Plan) without Intent to Act, Category 4 – Active Suicidal Ideation with Some Intent to Act, without Specific Plan, Category 5 – Active Suicidal Ideation with Specific Plan and Intent, Category 6 – Preparatory Acts or Behavior, Category 7 – Aborted Attempt, Category 8 – Interrupted Attempt, Category 9 – Actual Attempt (non-fatal), Category 10 – Completed Suicide.

Suicidal ideation is defined as a "yes" answer at any time during treatment to any one of the five suicidal ideation questions (Categories 1-5) on the C-SSRS. Suicidal behavior is defined as a "yes" answer at any time during treatment to any one of the five suicidal behavior questions (Categories 6-10) on the C-SSRS. Suicidal ideation or behavior is defined as a "yes" answer at any time during treatment to any one of the five suicidal behavior at any time during treatment to any one of the ten suicidal ideation and behavior questions (Categories 1-10) on the C-SSRS.

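### Exclusion 18 names suicidal behavior in the past 12 months, but only C-SSRS ideation items can trigger it

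*Protocol*

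**What the plan says.** Exclusion 18 in Protocol Section 7.2 excludes "Suicidal ideation or behavior in the past 12 months as indicated by a positive response (yes) to question 4 or 5 on the C-SSRS". Either the Screening or the Baseline assessment counts. The synopsis and SAP 4.2.2 repeat the criterion. Section 11.7 gives the same rule in operational form: a yes to item 4 or 5 at screening or baseline bars the patient, and no behavior item is mentioned.

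Appendix 13 prints the form. Question 4 is "Active Suicidal Ideation with Some Intent to Act, without Specific Plan", and question 5 adds a specific plan. Both stand in the ideation section. Attempts and preparatory acts are in a separate behavior section. SAP 12.7 makes the same split: categories 1 to 5 are ideation, and behavior is a yes to "any one of the five suicidal behavior questions (Categories 6-10) on the C-SSRS".

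On the look-back period, Section 11.7 describes two versions of the scale, "1 for use at screening referring to the past year" and one covering the time since the prior visit. On the printed screening form the recent column is headed 12 months for ideation but 12 years for behavior.

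**The concern.** The criterion promises to exclude on ideation or behavior but tests ideation only. Taken literally, ideation with some intent in the past year excludes a patient automatically, while a recorded attempt in the same year does not. That ordering is hard to defend in a trial whose Section 4.3.2 says patients at risk for suicide will be excluded, tells patients of a possible class risk of depression or suicidal thoughts, and reports one case of self-injury without suicidal intent on 40 mg in the psoriasis trial. What is at stake is the safety of enrolled patients and uniform application of eligibility across about 48 sites.

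**Working it through.** There is no stated figure to reproduce. The check is a comparison of texts and a count of items.

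**1. Which items the criterion reads.**

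| Form (Appendix 13) | Ideation items used | Suicidal behavior yes/no items used |
|---|---|---|
| Screening | 2 of 5 (questions 4 and 5) | 0 of 5 |
| Since last visit (Baseline) | 2 of 5 | 0 of 4 |

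The screening form has four types of behavior item: actual attempt, interrupted attempt, aborted or self-interrupted attempt, and preparatory acts. A summary item asks whether "Suicidal behavior was present during the assessment period", so 4 + 1 = 5. No summary item is printed on the since-last-visit form, which leaves 4. The item on non-suicidal self-injury is not counted. SAP categories 6 to 10 are the same four types plus completed suicide, which cannot apply at screening.

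**2. Whether behavior can be recorded without a yes to question 4 or 5.** The printed form allows it.

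- The instruction is "Ask questions 1 and 2. If both are negative, proceed to" the behavior section. Questions 3 to 5 are asked only after a yes to question 2. A patient who answers no to question 2 is therefore never asked questions 4 and 5, but is still asked about behavior.
- Under actual attempt, the form says of intent: "Even if an individual denies intent/wish to die, it may be" inferred clinically. An attempt can thus be recorded in a patient who denies the ideation.
- A patient can also answer yes to question 1 or 2, no to questions 4 and 5, and yes to a preparatory act.

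In each case exclusion 18 is not met.

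**3. What else would exclude such a patient.** Exclusion 8 lists suicidal behavior as an example, but it applies only if, in the Investigator's opinion, the condition would prevent adherence or completion or pose unacceptable risk. Exclusion 12 covers any condition that places the patient at unacceptable risk. Neither is linked to a C-SSRS answer. Compare depression: a HADS depression score of 15 or more is also an example in exclusion 8, but Section 11.6 separately makes it an automatic bar. Suicidal behavior has no such rule.

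**4. The column heading.** 12 years × 12 = 144 months, against 12 months in exclusion 18, a factor of 144 / 12 = 12. Because exclusion 18 does not read the behavior section, this heading changes no eligibility decision today. It would matter once a 12-month behavior trigger is added.

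**The case against.** The best defence is that this is a deliberate two-tier design: automatic exclusion for active ideation with intent, clinical judgement for behavior. Exclusion 8 names suicidal behavior, and the amendment summary shows that this detail was added in an amendment prompted by FDA recommendations. The C-SSRS is administered by the Investigator, so the person who records an attempt is also the person applying exclusions 8 and 12. The routes round questions 4 and 5 are narrow. An actual attempt requires at least some wish to die, which should usually bring a yes to question 1, and the form's examples of inferred intent are acts that few Investigators would judge an acceptable risk. During the study, a yes to any of questions 1 to 5 pauses the drug and leads to specialist referral, and suicidal behavior is an adverse event of special interest. Finally, the protocol says of the printed scales: "The assessments and scales included in the appendixes are samples of what may be used during the study". The 12-year heading may therefore not be on the form that sites use.

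Much of this stands as mitigation. The gap is between automatic and judged exclusion; it does not mean that such patients are simply admitted. The group is likely small, and the heading is a side issue. The two-tier reading, however, does not fit exclusion 18, whose own text claims to cover behavior. On-study monitoring acts only after enrolment, and its pause-and-refer rule is also keyed to the ideation questions. The sample status of the forms affects the skip rule, the inference rule and the heading. It does not affect the mismatch inside the criterion, which SAP 12.7 confirms independently.

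**Conclusion.** The concern holds. Exclusion 18 does not do what it says for suicidal behavior: 0 of the 5 behavior items on the screening form can trigger it, and the same omission appears in all four places where the rule is given. Patients with behavior in the past 12 months in whom question 4 or 5 is answered no, or is never reached, depend on Investigator judgement under exclusions 8 and 12. The number of such patients cannot be derived from the documents. Sample size, the primary analysis and the other efficacy analyses are unaffected. The item counts, the routes round questions 4 and 5 and the heading error assume that the form in use matches the printed one; the core mismatch does not. The change is worth making because it serves the protocol's own stated commitment at little cost.

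**What to change.** 1. In exclusion 18 (Section 7.2), the synopsis, Section 11.7 and SAP 4.2.2, change the trigger to: *a positive response to question 4 or 5, or to any suicidal behavior item (actual, interrupted or aborted attempt, or preparatory acts) in the past 12 months, on the C-SSRS*. The SAP edit only keeps the documents consistent; the protocol text governs enrolment.
2. On the Appendix 13 screening form, change the behavior column heading from 12 years to 12 months, and check the form used at sites for the same heading.

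Exclusions 8 and 12 and Section 4.3.2 can stay as they are.

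The cost is 4 text edits + 1 heading = 5 edits, a reissued form if the heading is live, and possibly a few more screen failures. No new assessment is needed, because the behavior items are already on the screening form.

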# 7.3 Rescreening

Individuals who sign the ICF to participate in the study but who do not subsequently meet all the requirements as outlined in the inclusion and exclusion criteria and therefore do not enroll (screen failures) may be rescreened. Such individuals may be allowed to rescreen up to one timet the investigator's discretion (period from screen failure to rescreening to be determined by the investigator). If rescreening is performed, the individual must sign a new ICF and will be assigned a new identification number. Additionally, all screening procedures must be conducted at rescreening to ensure all eligibility criteria are met.

## 7.4 Treatment Discontinuation and Withdrawal

An additional 22 patients will be randomized to account for an estimated early dropout rate of approximately 10%.

If a patient discontinues study treatment prematurely or is withdrawn from the study for any reason, the study site must immediately notify the Medical Monitor. The date and the reason for treatment discontinuation or study withdrawal must be recorded on the electronic case report form (eCRF). Patients who discontinue treatment prematurely will be asked to complete the assessments corresponding to Week 16 at the time of treatment discontinuation. The patient will be asked to return to the study site within 4 weeks of the last administration of study drug to complete the follow-up visit and have the assessments corresponding to the Week 20 assessments done (Table 4). If possible and deemed safe by the investigator, the patient should thereafter be offered to stay in the trial with no treatment and complete study visits as planned. If a patient withdraws from the study, attempts should be made to have him or her return to the study site within 4 weeks of study drug to complete follow-up visit assessments.

In the event that a patient discontinues treatment prematurely because of a TEAE or serious TEAE, this will be followed up until it resolves (returns to normal or baseline values) or stabilizes, or until it is judged by the Investigator to no longer be clinically significant. The patient will also be asked to return to the study site for the follow-up visit within 4 weeks of the last administration of study drug to have the assessments corresponding to the Week 20 assessments done (Table 4).

Once withdrawn from the study, the patient cannot re-enter the study.

A patient may voluntarily withdraw or be withdrawn from the study at any time for reasons including, but not limited to, the following circumstances:

- unacceptable toxicity or AE
- patient withdrawal of consent: at any time, a patient's participation in the study may be terminated at his/her request or on the basis of the investigator's clinical judgment. The reason for patient withdrawal will be noted on the eCRF

- intercurrent illness: a condition, injury, or disease unrelated to the primary diagnosis that became apparent during treatment and necessitated the patient's termination from the study
- general or specific changes in the patients' condition that renders him/her ineligible for further treatment according to the inclusion/exclusion criteria
- patient fails to adhere to the protocol requirements (eg, drug noncompliance, failure to return for defined number of visits)
- lost to follow-up: the patient stopped coming for visits, and study personnel were unable to contact the patient
- pregnancy, as indicated in Section 11.8.5.

If a patient withdraws from the study, the Sponsor may retain and continue to use any data collected before the withdrawal for the purpose of the study or scientific research.

Additionally, the Sponsor may stop the study at any time for safety, regulatory, legal, or other reasons aligned with Good Clinical Practice (GCP). This study may be terminated at the discretion of the Sponsor or any regulatory agency. An Investigator may elect to discontinue or stop the study at his or her study site for any reason, including safety or low enrollment.

